### Document History

Document	Version Date
Original protocol	18 October 2021

[figure not shown]

## 1. PROTOCOL SUMMARY

### 1.1. Synopsis

**Brief Title:** A Phase 1 Study to Evaluate the Effect of Hight-Fat Meal on the Relative Bioavailability of PF-07321332 Boosted with Ritonavir in Healthy Adult Participants

### Rationale

The purpose of the study is to evaluate the effect of a high-fat meal on the relative bioavailability of PF-07321332 boosted with ritonavir following a single dose oral administration of PF-07321332 in combination with ritonavir using 150 mg PF-07321332 tablet which was developed as the commercial drug product.

### Objectives and Endpoints

Objectives	Endpoints
Primary: 

To evaluate the effect of a high-fat meal on the exposures of PF-07321332 boosted with ritonavir following a single oral dose of PF-07321332 in combination with ritonavir using 150 mg tablet formulation of PF-07321332.

	Primary: 

The ratio of <math>AUC_{last}</math>, <math>AUC_{inf}</math> (if data permit) and <math>C_{max}</math> of PF-07321332.

Secondary: 

To characterize the pharmacokinetic parameters of PF-07321332 boosted with ritonavir following a single oral dose of PF-07321332 in combination with ritonavir.

To evaluate the safety and tolerability of PF-07321332/ritonavir in healthy participants.

	Secondary: 

<math>T_{max}</math>, and <math>t_{1/2}</math>, <math>CL/F</math> and <math>V/F</math> (if data permit).

Assessment of TEAEs, clinical laboratory abnormalities, vital signs, and 12-lead ECGs.

### Overall Design

#### Brief Summary

This is a Phase 1, open-label, single dose, randomized, 2-treatment, 2-sequence, 2-period crossover study to evaluate the effect of a high-fat meal on the relative bioavailability of PF-07321332 boosted with ritonavir following single dose oral administration of PF-07321332 in combination with ritonavir using 150 mg tablets of PF-07321332 in healthy adult participants. The study will consist of 2 treatments: a single oral dose of 300 mg PF-07321332 ( $2 \times 150$  mg tablets) under fasted conditions and 3 doses of 100 mg ritonavir at -12 hour, 0 hour and 12 hour related to PF-07321332 dosing (Treatment A), and a single oral dose of 300 mg PF-07321332 ( $2 \times 150$  mg tablets) under fed conditions and 3 doses of 100 mg ritonavir at -12 hour, 0 hour and 12 hour related to PF-07321332 dosing (Treatment B). Approximately 12 healthy male and/or female participants will be

randomized into 1 of 2 sequences. Participants who discontinue from the study for non-safety reasons may be replaced at the sponsor's discretion in collaboration with the Investigator.

Healthy participants will be screened to determine eligibility within 28 days prior to study treatment. Medical history and results of physical examination, physical measurements, vital signs, 12-lead ECGs, and clinical laboratory evaluations will determine eligibility. Participants will report to the CRU on Day -1, Period 1 and will be required to stay in the CRU for 8 days and 7 nights.

Eligible participants will be admitted to the CRU at least 12 hours prior to the dosing of PF-07321332 on Day 1. On the evening of Day -1, participants will receive a single oral dose of ritonavir 100 mg (-12 hour relative to PF-07321332/ritonavir dosing). On the morning of Day 1 of each period, participants will receive a single dose of PF-07321332 300 mg/ritonavir 100 mg as per randomization schedule. Study interventions will be administered with approximately 240 mL of ambient temperature water. In fed periods (Sequence 2, Period 1 and Sequence 1, Period 2), following an overnight fast of at least 10 hours, participants should begin breakfast approximately 30 minutes prior to PF-07321332/ritonavir administration. A high-fat (approximately 50% of total caloric content of the meal), high-calorie (approximately 800 to 1000 calories) breakfast will be consumed over approximately a 20-minute interval with PF-07321332/ritonavir administered within approximately 10 minutes of completion of the meal. Ritonavir, 100 mg, will continue to be dosed at 12 hours post PF-07321332 dosing. Serial PK samples will be collected up to 48 hours post dose. Period 2 will begin on Study Day 4 (referred to as Period 2, Day -1). Participants will be discharged from the CRU on Period 2, Day 3 following completion of all assessments.

If a participant has any clinically significant, study related abnormalities at the conclusion of a scheduled inpatient portion of the study, the Pfizer medical monitor (or designated representative) should be notified and the participant may be asked to remain in the CRU until such abnormalities are deemed not clinically significant, or it is safe for outpatient follow-up.

A safety follow-up call will be made to participants approximately 28 to 35 days from administration of the final dose of study intervention.

## **Number of Participants**

Approximately 12 participants will be randomly assigned to study intervention.

Note: "Enrolled" means a participant's, or his or her legally authorized representative's, agreement to participate in a clinical study following completion of the informed consent process and screening. A participant will be considered enrolled if the informed consent is not withdrawn prior to participating in any study activity after screening. Potential participants who are screened for the purpose of determining eligibility for the study, but do not participate in the study, are not considered enrolled, unless otherwise specified by the protocol.

## Intervention Groups and Duration

Each participant will be screened to determine eligibility within 28 days prior to study treatment. Eligible participants will report to the CRU on Day -1, Period 1 and will be required to stay in the CRU for 8 days and 7 nights. A safety follow-up call will be made to participants approximately 28 to 35 days from administration of the final dose of study intervention.

Each enrolled participant will participate in 2 study periods to receive 2 different treatments according to the sequence determined by randomization:

- Treatment A: Single oral dose of 300 mg PF-07321332 (2 × 150 mg tablets) under fasted conditions and 3 doses of 100 mg ritonavir at -12 hour, 0 hour and 12 hour related to PF-07321332 dosing. (Reference)
- Treatment B: Single oral dose of 300 mg PF-07321332 (2 × 150 mg tablets) under fed conditions and 3 doses of 100 mg ritonavir at -12 hour, 0 hour and 12 hour related to PF-07321332 dosing. (Test)

Participants will be randomly assigned to 1 of 2 sequences as follows:

	Period 1	Washout (4 days between PF-07321332 dosing)	Period 2
Sequence 1 (n=6)	Treatment A		Treatment B
Sequence 2 (n=6)	Treatment B		Treatment A

## Data Monitoring Committee or Other Independent Oversight Committee: None

## Statistical Methods

### Pharmacokinetics Analysis

The PK concentration population is defined as all participants randomly assigned to study intervention and who take at least 1 dose of study intervention and in whom at least 1 concentration value is reported.

The PK parameter analysis population is defined as all participants randomly assigned to study intervention and who take at least 1 dose of study intervention and in whom at least 1 of the PK parameters of interest are reported.

PK parameters for PF-07321332 will be analyzed using standard noncompartmental method of analysis. Actual PK sampling times will be used in the derivation of PF-07321332 PK parameters when available, otherwise nominal times will be used. The PF-07321332 plasma PK parameters will be summarized descriptively by treatment. Plasma concentrations will be listed and summarized descriptively by treatment, and nominal PK sampling time. Individual participant and summary profiles (mean and median plots) of the plasma concentration time data will be plotted by treatment using actual and nominal times, respectively.

Natural log transformed  $AUC_{inf}$  (if data permit),  $AUC_{last}$  and  $C_{max}$  will be analyzed using a mixed effect model with sequence, period and treatment as fixed effects and participant within sequence as a random effect. Estimates of the adjusted mean differences (Test-Reference) and corresponding 90% CIs will be obtained from the model. The adjusted mean differences and 90% CIs for the differences will be exponentiated to provide estimates of the ratio of adjusted geometric means (Test/Reference) and 90% CI for the ratios. Treatment A (PF-07321332/ritonavir administered under fasted condition) is the Reference treatment and Treatment B (PF-07321332/ritonavir administered under fed condition) is the Test treatment.

### **Safety Analysis**

All safety analyses will be performed on the safety analysis set, which is defined as all participants randomly assigned to study intervention and who take at least 1 dose of study intervention. Safety data will be presented in tabular and/or graphical format and summarized descriptively, where appropriate.

### **1.2. Schema**

Not applicable.

### 1.3. Schedule of Activities

The SoA table provides an overview of the protocol visits and procedures. Refer to the **STUDY ASSESSMENTS AND PROCEDURES** section of the protocol for detailed information on each procedure and assessment required for compliance with the protocol.

The investigator may schedule visits (unplanned visits) in addition to those listed in the SoA table, in order to conduct evaluations or assessments required to protect the well-being of the participant.

Visit Identifier Abbreviations used in this table may be found in Appendix 8	Screening a	Periods 1-2 b													28-35 days (Follow-Up)	Early Termination/Discontinuation	
		Day -1	Day 1														
Days Relative to Day 1	Days -28 to -2	0	0.5	1	1.5	2	2.5	3	4	6	8	12	16	24	48		
Hours After Dose																	
Informed consent	X																
CRU Confinement c		X	→	→	→	→	→	→	→	→	→	→	→	→	X		
Inclusion/exclusion criteria	X	X u															
Medical/medication history (update) d	X	X u															
Demography e	X																
Physical exam f	X	X u															
Safety laboratory (including aPTT, PT-INR, Fibrinogen, and eGFR) g	X	X u												X		X	
FSH h	X																
Urine drug testing i	X	X u															
Serology: HBsAg, HBsAb, HBcAb, HCVAb, and HIV j	X																
Pregnancy test (WOCBP only)	X	X u												X		X	
Contraception check k	X	X u													X		
Single supine 12-lead ECG l	X		X v											X		X	
Vital signs (BP/PR/RR/temperature) m	X		X v											X		X	
COVID-19 questionnaire n	X	X u															

PFIZER CONFIDENTIAL

Visit Identifier Abbreviations used in this table may be found in Appendix 8	Screening a	Periods 1-2 b													28-35 days (Follow-Up)	Early Termination/Discontinuation	
		Day -1	Day 1														
Days Relative to Day 1	Days -28 to -2	0	0.5	1	1.5	2	2.5	3	4	6	8	12	16	24	48		
Hours After Dose																	
COVID-19 testing o	X	X u															
Ritonavir administration b		X										X					
PF-07321332/ritonavir administration q			X														
PK Blood Sampling for PF-07321332 r			X	X	X	X	X	X	X	X	X	X	X	X	X	X	X
CCI																	
Serious and nonserious AE monitoring	X	→	→	→	→	→	→	→	→	→	→	→	→	→	→	X	X
Concomitant treatments			X	→	→	→	→	→	→	→	→	→	→	→	→	X	X
CRU discharge t																X	

- a. Screening will be performed within 28 days prior to the first dose of PF-07321332/ritonavir.
- b. Period 2 will begin on Study Period1, Day 4 (referred to as Period 2, Day -1).
- c. Participants will be admitted to the CRU at least -12 hours prior to PF-07321332 dose on Day 1. Participants will be discharged on Day 3 of Period 2 following the final assessments.
- d. Medical history will include a history of prior illegal drug, alcohol, and tobacco use, as well as blood donation within prior 60 days. Medical history will be recorded at screening and updated on Day -1 of Period 1.
- e. Demographics will include participant race, ethnicity, age, and gender during the screening visit.
- f. Physical exam will be performed by trained medical personnel at the investigator site at screening or Day -1 of Period 1 only (height and weight must be obtained at screening to obtain BMI for eligibility criteria). A targeted PE may be performed at other designated time points at the discretion of the investigator.
- g. Safety laboratory assessments including urinalysis, hematology, chemistry and coagulation will be performed at the indicated time-points. All the safety laboratory samples must be collected following at least a 4-hour fast. Additional safety laboratory assessments may be performed at any time at the discretion of the investigator.
- h. For postmenopausal (amenorrheic for at least 12 consecutive months) female participants only.
- i. Urine drug (mandatory) and alcohol breath test (at discretion of investigator) will be performed at screening and on Day -1. These tests may be performed at any other time at the discretion of the investigator.
- j. HBsAb will be tested if HBsAg and/or HBcAb are positive.
- k. The investigator or his/her designee will discuss with the participant the need to use highly effective contraception consistently and correctly according to contraception guidelines.
- l. All ECG assessments will be made after at least a 5 minute rest in a supine position and prior to any blood draws or vital sign measurements. Day 3 ECG for Period 2 only.
- m. Single supine BP, RR and PR will be performed following at least a 5 minute rest in a supine position. BP, RR and PR assessments will be performed after collection of ECGs and prior to collection of blood draws if scheduled at the same time. Day 3 measurements are for Period 2 only. Temperature will be measured as per CRU standard practice.

PFIZER CONFIDENTIAL

Visit Identifier Abbreviations used in this table may be found in Appendix 8	Screening a	Periods 1-2 b												28-35 days (Follow-Up)	Early Termination/Discontinuation			
Days Relative to Day 1	Days -28 to -2	Day -1	Day 1										Day 2	Day 3	Day 28-35 w			
Hours After Dose			0	0.5	1	1.5	2	2.5	3	4	6	8	12	16	24	48		

n. Check exposure to positive participant, residence or travel in area of high incidence and COVID-19 related signs and symptoms.

o. The testing for COVID-19 pathogen by RT-PCR will be performed at each visit. For participants admitted for residence, a subsequent COVID-19 test will be performed after 4 days (ie, upon completion of 4 x 24 hours in house), or if they develop COVID-19 like symptoms.

p. Ritonavir will be administered orally -12 hours and 12 hours relative to PF-07321332/ritonavir dosing on Day 1.

q. PF-07321332/ritonavir will be administered orally after overnight fasting on Day 1 of each treatment period.

r. One (approximately 4 mL) blood sample for PK analysis of PF-07321332 will be taken at the designated time points post dose in each dosing period.

t. Participants will be discharged after collection of the 48-hour PK sample of period-2 dosing.

u. Period 1 only.

v. Collected at pre-dose for Period 1 only.

w. Contact may occur via telephone and must occur 28 to 35 days from administration of the final dose of study intervention.

## 2. INTRODUCTION

PF-07321332 is a potent and selective inhibitor of the SARS-CoV-2 3CL protease that is currently being developed as an oral treatment of COVID-19. Ritonavir is a strong CYP3A4 inhibitor being used to inhibit the metabolism of PF-07321332 in order to increase plasma concentrations of PF-07321332 to values that are anticipated to be efficacious.

### 2.1. Study Rationale

The purpose of the study is to evaluate the effect of a high-fat meal on the relative bioavailability of PF-07321332 boosted with ritonavir following a single dose oral administration of PF-07321332 in combination with ritonavir using 150 mg PF-07321332 tablet which was developed as the commercial drug product. Results from this study will use to provide information for pre- and post-marketing.

### 2.2. Background

In December 2019, COVID-19 was identified as a new, potentially fatal, respiratory infection caused by the novel coronavirus, SARS-CoV-2. The WHO declared COVID-19 a Public Health Emergency of International Concern on 20 January 2020 and further characterized the disease outbreak as a pandemic on 11 March 2020.

[figure not shown]
PF-07321332 is an orally bioavailable 3CLpro inhibitor shown to be effective against SARS-CoV-2 3CLpro ( $K_i = 0.00311 \mu\text{M}$ ) in a biochemical enzymatic assay. Since the 3CLpro from human coronaviruses are structurally similar and share a high degree of conservation at the active site of the enzyme, the ability of PF-07321332 to inhibit the 3CLpro of other coronaviruses (SARS-CoV-1 and HCoV-229E, MERS, HCoV-OC43, HCoV-HKU1, and HCoV-NL63) was also confirmed, indicating a potential for broad spectrum anti-coronavirus activity. The coronavirus 3CL protease is a virally encoded enzyme that is critical to the SARS-CoV-2 replication cycle, analogous to other obligatory virally encoded proteases (eg, HIV Protease, HCV Protease). PF-07321332 is being developed as an oral treatment in patients with COVID-19 infection.

Ritonavir is a strong CYP3A4 inhibitor being used to inhibit the metabolism of PF-07321332 in order to increase plasma concentrations of PF-07321332 to values that are anticipated to be efficacious. Ritonavir is not expected to have any pharmacological impact on the SARS-CoV-2 virus and its elimination is not expected to be significantly altered by renal impairment. Ritonavir is being used only as a PK boosting agent.

The effect of a high-fat meal on the exposures of PF-07321332 following co-administration of PF-07321332 as a 250 mg oral suspension with 100 mg of ritonavir in healthy participants was evaluated in PART-1 of the FIH study C4671001. **CCI**

CCI

### **2.2.1. Nonclinical Pharmacology**

Details of the nonclinical pharmacology of PF-07321332 can be found in the current IB.

### **2.2.2. Nonclinical Pharmacokinetics and Metabolism**

Hepatic CYP3450 enzymes were identified as the main pathway for clearance of PF-07321332 in vitro in liver microsomes (mouse, rat, hamster, rabbit, monkey, and human), hepatocytes (rat, monkey, and human), and in vivo in rat and monkey after repeat oral dosing. In a reaction phenotyping study using human liver microsomes in the presence of selective CYP inhibitors, CYP3A4 was predicted to be the major contributor ( $f_m = 0.99$ ) to the in vitro oxidative metabolism of PF-07321332. No significant CYP3A5 contribution is expected to the metabolism of PF-07321332.

Additional information of the nonclinical PK and metabolism of PF-07321332 is available in the current IB.

### **2.2.3. Nonclinical Safety**

There were no adverse findings observed in repeat-dose toxicity studies in rats and monkeys up to two weeks duration and the NOAELs were the highest dose administered (1000 mg/kg and 600 mg/kg in the rat and monkey studies, respectively). PF-07321332-related non-adverse, test article-related clinical findings included sporadic occurrence of emesis with slight body weight decreases in monkeys. Monitorable and reversible clinical pathology findings included those possibly suggestive of low-grade inflammation (in rats and monkeys) or alterations in the coagulation pathways (in rats only) without clinical or microscopic correlates. Other non-adverse clinical pathology findings were likely due to the emesis and subsequent dehydration in monkeys. In rats administered 1000 mg/kg/day, lower mean absolute and relative heart weights (females) and higher absolute and relative liver weights (both sexes) were observed relative to controls. The lower heart weights had no microscopic correlates and were fully reversed at the end of the 2-week recovery period. Higher liver weights correlated with reversible, non-adverse microscopic findings of minimal to mild severity in the liver and thyroid gland consistent with adaptive changes related to microsomal enzyme induction.

[figure not shown]
[figure not shown]
[figure not shown]
PF-07321332 was not mutagenic or clastogenic in in vitro genetic toxicity studies and was negative in the in vivo rat micronucleus assay incorporated into the GLP repeat-dose rat toxicity study.

The nonclinical studies performed adequately support the oral administration of PF-07321332 in the clinic for up to 14 days.

[figure not shown]
[figure not shown]
Further details of the nonclinical safety program are provided in the current IB.

#### 2.2.4. Clinical Overview

[figure not shown]
[figure not shown]
Safety, tolerability and PK of PF-07321332 in healthy adult participants was explored in Phase 1 FIH Study (C4671001). Study C4671001 was a five-part study consisting of SAD (PART-1), MAD (PART-2), relative bioavailability/food effect (PART-3), metabolism and excretion study (PART-4) and supratherapeutic exposure cohort (PART-5). PART-1 and -2 are randomized, double-blind, sponsor-open, and placebo-controlled to evaluate safety, tolerability, and PK of single and multiple escalating oral doses of PF-07321332, respectively. PART-3 was randomized and open-label to evaluate relative bioavailability and food effect of an oral tablet formulation. PART-4 is an open-label, non-randomized, single-period to evaluate the metabolism and excretion of PF-07321332. PART-5 was a double-blind, sponsor-open, randomized, cross-over study to evaluate safety and tolerability at supratherapeutic exposures. **CCI**

CCI

CCI

CCI

### 2.3. Benefit/Risk Assessment

PF-07321332/ritonavir are not expected to provide any clinical benefit to healthy participants in this study. This study is designed primarily to estimate relative bioavailability of PF-07321332 150 mg tablet compared to PF-07321332 100 mg tablet formulation in healthy adult participants and bridge PK between these 2 formulations.

More detailed information about the known and expected benefits and risks and reasonably expected adverse events of PF-07321332 may be found in the IB, which is the SRSD for PF-07321332. The SRSD for ritonavir is USPI.

### 2.3.1. Risk Assessment

Potential Risk of Clinical Significance	Summary of Data/Rationale for Risk	Mitigation Strategy
Study Intervention(s) PF-07321332		
Emesis	Sporadic emesis was observed at $\geq 100$ mg/kg/day of PF-07321332 in the 15-day NHP toxicology study (See IB). CC1 [REDACTED]	As this is an investigational agent, there is some risk that is mitigated by close observation of AEs, etc. If needed, palliative care or antiemetics may be provided.
Neuronal and pulmonary effects	Transient effect in rat neuronal and pulmonary endpoints were observed in rat toxicology study at the high dose level (1000 mg/kg as single dose; See IB). CC1 [REDACTED]	Vital signs, including respiratory rate, will be monitored for pulmonary effect. There will be close observation of AEs for any signs of neuronal effect.
Hemodynamic effects	Low level inflammation (increase in fibrinogen) in 15-day NHP toxicology study and changes in platelets, globulin and albumin/globulin ratio and coagulation system (increase in PT and aPTT) in 14-day rat toxicology study (See IB). CC1 [REDACTED]	Fibrinogen, platelets, PT-INR and aPTT, albumin and total proteins will be monitored.

PFIZER CONFIDENTIAL

Potential Risk of Clinical Significance	Summary of Data/Rationale for Risk	Mitigation Strategy
	CCI [REDACTED]	
Study Intervention(s) Ritonavir		
Gastrointestinal disturbances (including diarrhea, nausea, vomiting and abdominal pain).	Frequently reported adverse reaction in HIV patients at 600 mg BID.	Lower dose of 100 mg twice daily is used in this study. There will be close observation of AEs. If needed, anti-emetics may be provided.
Neurological disturbances (eg, paresthesia, including oral paresthesia, dysgeusia and dizziness).	Frequently reported adverse reaction in HIV patients at 600 mg BID.	Lower dose used in this study. There will be close observation of AEs.
Rash (most commonly reported as erythematous and maculopapular, followed by pruritic).	Frequently reported adverse reaction in HIV patients at 600 mg BID.	Lower dose used in this study. There will be close observation of AEs and monitoring through targeted physical exams. If needed, palliative care may be provided.
Fatigue/Asthenia	Frequently reported adverse reaction in HIV patients at 600 mg BID.	Lower dose used in this study. There will be close observation of AEs and monitoring through targeted physical exams.
Limited case reports of renal toxicity	Although ritonavir therapy is not generally considered nephrotoxic, a limited number of cases of acute kidney injury secondary to ritonavir have been reported post-marketing in HIV patients.	Lower dose used in this study. There will be close observation of AEs and renal function.

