### 2.3.3. Overall Benefit/Risk Conclusion

PF-07321332/ritonavir is not expected to provide any clinical benefit to healthy participants in this study. Taking into account the measures taken to minimize risk to participants of this study, the potential risks identified in association with PF-07321332/ritonavir are justified by the anticipated benefits, in terms of contribution to the process of developing a new therapy in an area of unmet medical need.

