### **5.3.3. Activity**

- Participants will abstain from strenuous exercise (eg, heavy lifting, weight training, calisthenics, aerobics) for at least 48 hours prior to each blood collection for clinical laboratory tests. Walking at a normal pace will be permitted;
- In order to standardize the conditions on PK sampling days, participants will be required to refrain from lying down (except when required for BP, respiratory rate, pulse rate, and ECG measurements), eating, and drinking beverages other than water during the first 4 hours after PF-07321332/ritonavir dosing;
- Participants will be confined to the procedure room for the first 4 hours after dosing on Day 1, except to use the bathroom. After this, participants may be ambulatory but should not engage in strenuous activities.

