### **8.2.2. Vital Signs**

Supine BP will be measured with the participant's arm supported at the level of the heart and recorded to the nearest mm Hg after approximately 5 minutes of rest. The same arm (preferably the dominant arm) will be used throughout the study. Participants should be instructed not to speak during measurements.

The same properly sized and calibrated BP cuff will be used to measure BP each time. The use of an automated device for measuring BP and pulse rate is acceptable; however, when done manually, pulse rate will be measured in the brachial/radial artery for at least 30 seconds. When the timing of these measurements coincides with a blood collection, BP and pulse rate should be obtained prior to the nominal time of the blood collection.

Additional collection times, or changes to collection times, of BP and pulse rate will be permitted, as necessary, to ensure appropriate collection of safety data.

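### Protocol 2.3.1 relies on respiratory-rate monitoring for a transient pulmonary effect, but the only routine post-dose reading is 48 h after the second dose

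*Protocol*

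**What the plan says.** The risk table in Protocol 2.3.1 describes the finding as "Transient effect in rat neuronal and pulmonary endpoints were observed in rat toxicology study at the high dose level", namely 1000 mg/kg as a single dose. For the pulmonary part it names one mitigation: "Vital signs, including respiratory rate, will be monitored for pulmonary effect". The sentence after it ties AE observation to neuronal effects. Section 2.3.3 then draws its benefit/risk conclusion "Taking into account the measures taken to minimize risk to participants of this study".

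Timing is set by the SoA (Protocol 1.3). Its vital-signs row, which includes RR, has a mark at screening, one at hour 0, one later on study and one at early termination. Footnote v says of the hour-0 set: "Collected at pre-dose for Period 1 only". Footnote m says: "Day 3 measurements are for Period 2 only". Protocol 8.2 and SAP 3.5.3 both refer back to the SoA and add no times.

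Two other places bear on this. Section 5.3.3 tells participants to "refrain from lying down (except when required for BP, respiratory rate, pulse rate, and ECG measurements") during the first 4 h after dosing, so it anticipates RR readings in that window. Section 8.2.2 says "Additional collection times, or changes to collection times, of BP and pulse rate will be permitted" as necessary, without naming RR.

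**The concern.** A reader of 2.3.1 would expect RR to be measured at a time when a transient drug effect could be seen. The schedule offers a pre-dose value and a value two days after the last PF-07321332 dose. A short-lived change in RR without symptoms could come and go in either period with no planned reading to show it.

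The participants are healthy volunteers with no expected benefit, and 2.3.3 rests on the mitigations listed. An ethics committee should be able to take the risk table as a description of what will be done. Vital signs are also a secondary safety endpoint, and SAP 3.5.3 defines change from baseline in RR. For completers, that change has one scheduled post-dose value, far from exposure. The primary PK analysis is not affected.

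**Working it through.** **Inputs**
- Vital-signs times: SoA vital-signs row with footnotes m and v.
- Day 3 is the 48 h visit: SoA header, and footnote t (discharge after the 48 h PK sample of Period 2).
- Interval between PF-07321332 doses: 4 days = 96 h (Protocol 4.1, Table 1).
- Half-life with ritonavir: about 6 to 13 h (Protocol 4.2).
- Planned size: 12 participants, 6 per sequence, 2 periods each. All are assumed to complete.

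**Step 1. Scheduled RR after screening, for a completer**

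| Time relative to PF-07321332 dose | Period 1 | Period 2 |
|---|---|---|
| Pre-dose | yes (footnote v) | none |
| 0.5 to 24 h | none | none |
| 48 h (Day 3) | none (footnote m) | yes |

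The 48 h timing is taken from the footnotes and the Day 3 header, not from cell position in the table.

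**Step 2. Counts**
- Dosed periods: 12 × 2 = 24.
- Periods with a scheduled post-dose RR by 24 h: 0 of 24.
- Periods with a scheduled post-dose RR at any time: 12 of 24, all Period 2. By Table 1, 6 of these follow fed dosing and 6 follow fasted dosing.
- The single post-dose reading comes 96 + 48 = 144 h after the first dose.
- For comparison, PK draws in the first 4 h are at 0.5, 1, 1.5, 2, 2.5, 3 and 4 h, which is 7 per period.

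**Step 3. How far from exposure 48 h is**
- Half-lives elapsed = 48 / t½: 48/13 = 3.7 and 48/6 = 8.0.
- Fraction remaining = 0.5^(48/t½): 0.077 (7.7%) at 13 h and 0.004 (0.4%) at 6 h.

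This assumes first-order decline from the time of dosing. Absorption delays the decline, so the true fraction would be somewhat higher. The conclusion needs only that 48 h is late in the profile.

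**The case against.** The best case for the plan has four parts.

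- **Section 2.3.1 states no time or frequency.** RR is taken before dosing and at 48 h of Period 2, and whether that is enough is a clinical judgement. This is fair, and it makes the point one of adequacy. But the risk is described as transient, and a lone reading 3.7 to 8.0 half-lives after dosing does little to monitor such an effect.
- **The human evidence is redacted.** Text in the same table row and in the clinical overview (2.2.4) is blacked out, and the first-in-human study included a supratherapeutic cohort. Those data may show that close monitoring is unnecessary. They could justify dropping the measure, but not naming one that the schedule does not deliver near exposure.
- **Other safeguards exist.** Participants are confined and AEs are monitored throughout. An AE can stop dosing (7.1), and safety issues go to the sponsor at once (Section 8). This stands. A reader might infer that the second dose is given with no safety information from the first, and the documents do not support that. What is missing is a routine RR reading between the two doses.
- **RR can be added.** A reader might infer from 8.2.2, which names only blood pressure and pulse rate, that there is no route to an extra RR. That is wrong. The SoA introduction allows unplanned visits to protect participants. Footnote f allows a targeted physical examination at the investigator's discretion. Section 8.4.1 lets time points for planned assessments be added, with documentation and approval, without an amendment. SAP 6.6.3 counts unplanned post-dose time points. These routes are discretionary, however, and do not amount to planned monitoring. The same holds for the early-termination set, which is triggered by discontinuation.

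One could add that an extra reading has no action threshold, since SAP Appendix 1 has no RR category, and that a Period 2 reading would be compared with a baseline about four days old. Both are true. Still, Protocol 10.3.1 already makes a clinically significant vital-sign abnormality an AE, so an abnormal Period 1 reading would have a path to action before the second dose.

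**Conclusion.** The point holds and is minor. The mitigation stated in 2.3.1 is not matched by a routine RR reading near exposure in either period: 0 of 24 dosed periods have one by 24 h, and the only scheduled post-dose value is at 48 h of Period 2. This assumes 12 completers and the reading of footnotes m and v given above.

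A reader might go further and infer that participants are at material risk or are unmonitored. The documents do not support that. The dose is below the highest studied in the first-in-human trial (4.3), the rat finding was at a high dose, AE observation is continuous, and unscheduled checks are open to the investigator. Actual risk is probably low, although its size cannot be judged while the human data are redacted. What needs correcting is the gap between the stated measure and the schedule.

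**What to change.** **Preferred.** In the SoA vital-signs row and footnote m, add one set of blood pressure, pulse rate and RR in each period within 4 h after PF-07321332 dosing, immediately before a scheduled PK draw. The sponsor should pick the draw nearest the expected Tmax from its earlier data, which these documents do not show. Two consequential edits:
- Section 6.1.1 repeats the no-lying-down rule but omits RR from its exceptions. Align it with 5.3.3.
- Section 8 asks for blood pressure and pulse rate before any IV catheter is inserted. If catheters are used, exempt this set.

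The cost is 12 × 2 = 24 sets. Each needs about 5 minutes of supine rest, with the 30-second count taken during that rest (8.2.2.1). The setting is already in place: "Participants will be confined to the procedure room for the first 4 hours after dosing on Day 1", with 7 PK draws in that window. No blood or ECG is added, and fed and fasted periods are treated alike.

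**Alternative.** If earlier clinical data make the reading unnecessary, reword 2.3.1 to say that pulmonary effects are followed through AE observation, with on-study vital signs taken only before the first dose and 48 h after the second, and cite those data. This costs a change of wording, and 2.3.1 then states a weaker mitigation.
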